6.2.1 Specimen submission using the Alliance Biospecimen Management System

USE OF THE ALLIANCE BIOSPECIMEN MANAGEMENT SYSTEM (BioMS) IS MANDATORY AND ALL SPECIMENS MUST BE LOGGED AND SHIPPED VIA THIS SYSTEM.

BioMS is a web-based system for logging and tracking all biospecimens collected on Alliance trials. Authorized individuals may access BioMS at the following URL: [REDACTED] using most standard web browsers (Safari, Firefox, Internet Explorer). For information on using the BioMS system, please refer to the 'Help' links on the BioMS webpage to access the on-line user manual, FAQs, and training videos. To report technical problems, such as login issues or application errors, please contact: [REDACTED]. For assistance in using the application or questions or problems related to specific specimen logging, please contact: [REDACTED].

After logging collected specimens in BioMS, the system will create a shipping manifest. This shipping manifest must be printed and placed in the shipment container with the specimens.

All submitted specimens must be labeled with the protocol number (A211401), Alliance patient number, patient's initials and date and type of specimen collected (e.g., serum, whole blood).

A copy of the Shipment Packing Slip produced by BioMS must be printed and placed in the shipment with the specimens.

Instructions for the collection of samples are included below. Please be sure to use a method of shipping that is secure and traceable. Extreme heat precautions should be taken when necessary.

Ship specimens on Monday through Thursday only. Shipping by overnight service to assure receipt is encouraged. Do not ship specimens on Fridays or Saturdays [unless lab specifies Saturday delivery].

All specimens should be sent to the following address:

6.2.2 Saliva sample collection and submission

For patients enrolled on study, saliva samples will be obtained to analyze for cotinine as described in Section 14.1. Samples may be batched, but should be submitted at least every 3 months.

Saliva collection procedures for sites:

1. Confirm that SalivaBio Passive Drool Method collection kit is available. (Please find order information at [redacted]).

Kits may also be ordered from Fisher Scientific:

2. Document the presence of any significant oral infection or injury.
3. Patient should rinse mouth well with water about 5 minutes prior to collection to remove any food residue. Repeat if needed. No food or liquid intake before saliva collection.
4. Patient saliva should be collected following the kit instruction to get about 0.5-1ml saliva and freeze saliva samples at -20° C within 30 minutes or sooner if possible.
5. Document time between collection and placement in freezer.
6. Saliva samples should be kept frozen at -20° C until shipping samples to the Mayo Clinic biorepository, who will then batch shipments (every 6 months) to [name] at the Medical University of South Carolina for quantitative cotinine analyses.

Label samples with the following identification:

1. Alliance study number (A211401)
2. Alliance patient ID number
3. Patient's initials (L, F M)
4. Date and time of specimen procurement
5. Sample type (i.e. saliva)

6.2.3 Blood sample submission

For patients who consent to participate, blood samples will be used for the biomarker and pharmacogenomics analyses described in Section 14.2. Samples may be batched, but should be submitted at least every 3 months.

Collect 2 x 10 mL of peripheral venous blood in EDTA vacutainer tubes at the baseline visit.

Plasma: Centrifuge whole blood at 1,300 x g for 5 minutes at room temperature. Transfer 1 mL of plasma into each labeled 2 mL cryovial. Typically one can get 3 x 1 mL aliquots per 10 mL tube without disturbing the buffy coat (which will be saved for submission per the instructions below). Record the number of aliquots created on the Biospecimen Submission Form (BSF) Transfer plasma specimens to temporary storage at -80 °C until shipment. If there are no -80°C freezers available, keep the plasma samples on dry ice for up to 48 hours before shipment. Ship on dry ice to the Alliance Biorepository at Mayo clinic per Section 6.2.1.

Label samples with the following identification:

1. Alliance study number (A211401-PP1)
2. Alliance patient ID number
3. Patient's initials (L, F M)
4. Date and time of specimen procurement
5. Sample type (i.e. plasma)

Buffy coat: After the plasma has been removed from the vacutainer tube as described above, remove the buffy coat layer (approximately 1 mL per 10 mL EDTA tube) and transfer into 2 mL cryovial(s). Snap freeze specimen in LN2 or EtOH / dry ice bath OR place in - 80°C if the others are not available. Transfer specimen to temporary storage at -80°C until shipment. If there are no -80°C freezers available, keep the plasma samples on dry ice for up to 48 hours before shipment. Ship on dry ice to the Alliance Biorepository at Mayo clinic per Section 6.2.1.

Label samples with the following identification:

1. Alliance study number (A211401-PP1)
2. Alliance patient ID number
3. Patient's initials (L, F M)
4. Date and time of specimen procurement
5. Sample type (i.e. buffy coat)

7.0 TREATMENT PLAN/INTERVENTION

7.1 Study outline

It is understood that clinic practices may vary with respect to how patients eligible for this study are identified and treated. The following outline of study procedures has been provided to guide participating institutions with respect to the order of events for this trial.

Screening: It is expected that at the time patients are referred to the surgical clinic (e.g., from pulmonary or interventional radiology service, primary care physicians), they will be screened for this study. Alternatively, site staff may review internal medical records to identify patients eligible for the study who have not yet completed the surgical consult. Time permitting, pre-registration tests, observations, and questionnaires may be completed on the same day as registration/randomization and the Baseline Visit.

Surgical Consult: The surgical consult may be done as part of the screening process. It must be completed prior to registration/randomization. PLEASE NOTE: The No-Smoking Message can only be delivered AFTER registration/randomization, as this is part of the study intervention

Registration/Randomization: Patients must be registered/randomized following informed consent and prior to the Baseline Visit (see below).

Baseline Visit: The Baseline Visit will include the delivery of the No-Smoking Message by the Surgical Team Member, collection of saliva for cotinine measurement, baseline assessments per Section 5.1, and the completion of the baseline questionnaires.

7.2 Behavioral Intervention (Baseline visit)

Teachable Moment – No-Smoking Message from Surgical Team Member: This message will be given to all patients on study during the Baseline Visit, and can be delivered by the surgeon or by a designated surgical team member. This message contains the following key sections:

- (1) There is no better time to quit than when you are having cancer surgery;
- (2) Unique detriments of smoking in patients facing cancer surgery: a) tobacco-related carcinogenesis/pre-malignant to malignant progression; b) increased risks of perioperative morbidity or mortality; c) increased risk for surgical complications and wound healing time; d) possible decrease in the effectiveness of adjunctive cancer treatments and increased side effects of these treatments; e) increased risk of secondary cancers;
- (3) The best time to stop smoking is now;
- (4) We know it is difficult and many other health care professionals are ready to help you do this; and
- (5) The study team will be in contact with you periodically throughout the course of the study.

QUITLINE: Quitlines are an approved and cost-effective smoking cessation behavioral intervention[76] Quitlines are recommended by the US Smoking Cessation Guidelines[1] for their wide reach in large populations. The quitline selected to be used in this study can continue to be used by each study site long after the study is complete as it is free of charge to all. Support will be provided by the National Cancer Institute Telephone Smoking Quitline, [name], ([name]). This is a toll free telephone line within the United States and provides smoking cessation counseling Monday through Friday 8 am to 8 pm Eastern time. After randomization, the study staff will assist the patient in making the first contact with the quitline.

HANDOUT: All patients will also receive a handout with reminders of why they should stop smoking (message from surgeon) and quitline information.

7.3 Target Quit Date

Following the baseline visit, patients will receive the full 12 week supply of drug. The target quit date (TQD) is to be determined during the baseline visit and should occur prior to the planned date of surgery. It must be at least 10 days after randomization. While it is understood that it is rare for surgery in this patient population to be delayed, in order to allow for flexibility in exigent circumstances, the maximum time from randomization to the TQD will be 12 weeks.

7.4 Pharmacologic Intervention (Varenicline)

The initiation of the one-week dose escalation period of varenicline/placebo treatment will be considered Day 1 and the target quit date (one week later) will thus be Day 8 of therapy. Patients will be provided with instructions on the proper use of the medication (i.e., time of day to take the medication).

During Week 1, the dosing will be one of the 0.5 mg varenicline/placebo pills per day for the first 3 days followed by two 0.5 mg pills a day (morning and evening) for the next 4 days.

Weeks 2-12: Day 8 is the target quit day and on this day the patient will take two 0.5 mg pills twice daily (morning and evening). Patients will stay on this dose for 11 weeks.

Agent	Dose	Route	Day	
Varenicline/Placebo	0.5 mg	Oral	Days 1-3	1 pill per day
Varenicline/Placebo	0.5 mg	Oral	Days 4-7	1 pill twice per day – Minimum of 8 hours apart
Varenicline/Placebo	0.5 mg	Oral	Days 8-84	2 pills twice per day – Minimum of 8 hours apart (4 pills per day total)

Dosing should occur with 240 mL of water and it is recommended that patients eat prior to dosing to decrease gastric upset. It is recommended that there be at least 8 hours between the morning and evening dosing. If a dose is missed, the patient should take it as soon as s/he remembers. If it is almost time for the next dose (within 6 hours), the patient should skip the missed dose and take the next one as scheduled. Patients should not take a double dose of varenicline/placebo.

Participating institutions should have a suicide ideation monitoring and response procedures in place. An example of such procedures has been provided in Appendix XI.

8.0 DOSE AND TREATMENT MODIFICATIONS, UNBLINDING

8.1 Ancillary therapy, concomitant medications, and supportive care

8.1.1 Patients should not receive any other agent which would be considered treatment for smoking which can impact the primary endpoint. This includes, any nicotine replacement products (patch, gum, nasal spray, inhaler), bupropion, naltrexone,

8.1.2 Adjuvant chemotherapy and radiation therapy with curative intent for patients enrolled to this study is permitted.

8.1.3 Patients should receive full supportive care while on this study. This includes blood product support, antibiotic treatment, and treatment of other newly diagnosed or concurrent medical conditions. All blood products and concomitant medications such as antidiarrheals, analgesics, and/or antiemetics received from the first day of study treatment administration until 30 days after the final dose will be recorded in the medical records.

8.1.4 Diarrhea management is per the discretion of the treating physician. Diarrhea could be managed conservatively with medications such as loperamide.

8.1.5 Alliance Policy Concerning the Use of Growth Factors

Blood products and growth factors should be utilized as clinically warranted and following institutional policies and recommendations. The use of growth factors should follow published guidelines of the American Society of Clinical Oncology 2006 Update of Recommendations for the Use of White Blood Cell Growth Factors: An Evidence-Based, Clinical Practice Guideline. *J Clin Oncol* 24(19): 3187-3205, 2006.

8.2 Dose Modifications

The following general guidelines apply to all adverse events except suicidal ideation or personality change (see Sections 8.2.7 and 8.2.8). Additional information regarding insomnia and nausea is provided in Sections 8.2.5 and 8.2.6.

- All missed doses should be considered as skipped and not delayed. That is, the duration of treatment must not continue past the original 12-week stop date.
- Patients may be re-challenged only one time for grade 3 events. That is, if a particular adverse event recurs after a dose reduction and rechallenge, varenicline/placebo will be permanently discontinued.
- If treatment is skipped for more than four weeks due to toxicity, permanently discontinue varenicline/placebo.

8.2.1 Dose Levels

Dose Level 0	0.5 mg x 2 tablets twice daily
Dose Level -1	0.5 mg x 2 tablets once daily
Temporary discontinuation	

8.2.2 For Grade 1 or 2 adverse events possibly related to varenicline, will be followed per physician's discretion. Also, At the physician's discretion, varenicline/placebo dose may be continued, reduced to Dose Level -1, or be temporarily discontinued.

Re-challenge:

- If varenicline/placebo dose is reduced or temporarily discontinued, patients may be re-challenged at the physician's discretion to the next higher dose level the adverse event remains at grade 2 or better.
- If varenicline/placebo was temporarily discontinued and the patient was successfully rechallenged to Dose Level -1 and the adverse event remains at grade 2 or better after an additional week, the dose of varenicline/placebo may be resumed at Dose Level 0 at the discretion of the treating physician.

8.2.3 For Grade 3 adverse events possibly related to varenicline, patients will temporarily discontinue varenicline/placebo and will be assessed weekly until toxicity resolves to Grade 2 or better. Assessments may be done by telephone per institutional practices.

Re-challenge:

- If the adverse event has resolved to grade 0, the patient should restart varenicline/placebo at Dose Level -1.

- If the adverse event has improved to grade 1 or 2, patients may be re-challenged at the physician's discretion to Dose Level -1. If the adverse event remains at grade 2 or better after an additional week, the dose of varenicline/placebo may be resumed at Dose Level 0 at the discretion of the treating physician

8.2.4 For any Grade 4 adverse events, permanently discontinue varenicline/placebo.

8.2.5 Insomnia: If the reported adverse event is persistent sleeplessness, the patient may be instructed take his/her medication earlier in the day (8 hours after morning dose). If reducing to Dose Level -1, patients should skip the evening dose.

8.2.6 Nausea: If the reported adverse event is persistent nausea with morning medication, patients should be advised to do the following:

- Take varenicline/placebo on a full stomach (after eating).
- Drink an 8-ounce glass of water after taking the pill.
- Eat a banana.

If reducing to Dose Level -1, patients should skip the morning dose..

8.2.7 Suicidal ideation: Varenicline is known to cause suicidal ideation, patients must be screened for suicidal ideation at Weeks 6, 12, 18, and 24. If a patient responds with a positive (1+) response to question 9 on the PHQ9, s/he will be evaluated by a physician using the CTCAE.

Any patient with CTCAE grade 2 or higher suicidal ideation will immediately discontinue treatment with varenicline/placebo and be referred to a mental health professional in accordance with institutional guidelines. For reference, the CTCAE grades 1 through 4 for suicidal ideation are provided below:

Grade 1: Increased thoughts of death but no wish to kill oneself

Grade 2: Suicidal ideation with no specific plan or intent

Grade 3: Specific plan to commit suicide without serious intent to die which may not require hospitalization

Grade 4: Specific plan to commit suicide with serious intent to die which requires hospitalization

8.2.8 Personality Change: Any patient with CTCAE grade 3 or greater personality change will discontinue treatment with varenicline/placebo and be referred to a mental health professional in accordance with institutional guidelines. For reference, the CTCAE grades 1 through 4 for personality change are provided below:

Grade 1: Mild personality change

Grade 2: Moderate personality change

Grade 3: Severe personality change; hospitalization not indicated

Grade 4: Life-threatening consequences, threats of harm to self or others; hospitalization indicated

8.2.9 Somnambulism: Any patient experiencing sleep walking will discontinue treatment with varenicline.

8.2.10 Pregnancy: Varenicline/placebo will be immediately permanently discontinued for any patient who becomes pregnant during the treatment period of the study.

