3.2 Eligibility Criteria

Use the spaces provided to confirm a patient’s eligibility by indicating Yes or No as appropriate. It is not required to complete or submit the following pages.

When calculating days of tests and measurements, the day a test or measurement is done is considered Day 0. Therefore, if a test were done on a Monday, the Monday four weeks later would be considered Day 28.

- ___ **3.2.1** Eligible patients will have either confirmed or suspected new diagnosis of lung cancer and have sought a surgical consult relating to this diagnosis.
- ___ **3.2.2** Surgery must be scheduled no sooner than 10 days after randomization and no more than twelve weeks after randomization
- ___ **3.2.3** Have smoked daily or nearly every day in the previous 6 months up to the date of surgical consult AND have smoked at least one puff in the previous 7 days.
- ___ **3.2.4** Motivated to stop smoking, as indicated by a score of 6 or above on the Contemplation Ladder (see Appendix III).76

- ___ **3.2.5** Within the 30 days before registration, no use of: 1) any pharmacologic treatment for smoking cessation, including bupropion or nicotine replacement therapy; 2) any nicotine delivery system (i.e., e-cigarettes and vape products); or 3) be enrolled in any formal behavioral treatment program for tobacco dependence as determined by patient report.
- ___ **3.2.6** No allergies to and not currently using varenicline.
- ___ **3.2.7** No suicidal thoughts as indicated by a positive (1+) response to question 9 on the PHQ9.
- ___ **3.2.8** No active untreated clinically significant psychiatric condition (psychosis, bipolar disorder, or depression).
- ___ **3.2.9** Negative pregnancy test (serum or urine) done ≤ 7 days prior to registration, for women of childbearing potential only.
- A female of childbearing potential is a sexually mature female who: 1) has not undergone a hysterectomy or bilateral oophorectomy; or 2) has not been naturally postmenopausal for at least 12 consecutive months (i.e., has had menses at any time in the preceding 12 consecutive months).
- ___ **3.2.10** No unstable angina, myocardial infarction, or coronary angioplasty within the past 3 months or an untreated cardiac dysrhythmia.
- ___ **3.2.11** No history of seizures.
- ___ **3.2.12** No unstable neurologic, hepatic, renal, cardiovascular, lymphatic, or metabolic disease.
- ___ **3.2.13** Not currently on renal dialysis or has a history of significant renal impairment.

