Commercial varenicline capsular, biconvex tablets contain 0.5 mg (white to off-white, debossed with “Pfizer” on one side and “CHX 0.5” on the other side). Each 0.5 mg varenicline contains 0.85 mg of varenicline tartrate equivalent to 0.5 mg of varenicline free base. The following

inactive ingredients are included in the tablets: microcrystalline cellulose, anhydrous dibasic calcium phosphate, croscarmellose sodium, colloidal silicon dioxide, magnesium stearate, Opadry® White (for 0.5 mg), Opadry® Blue (for 1 mg) and Opadry® Clear.

Storage and Stability

Store at 25°C (77°F); excursions permitted to 15–30°C (59–86°F) (see USP Controlled Room Temperature).

Administration

Varenicline/placebo will be administered at a dosage of 0.5 mg once daily for 3 days, increasing to 0.5 mg twice daily for days 4 to 7, and then to the maintenance dose of 0.5 mg 2 tablets twice daily for up to 12 weeks of treatment. Patients should be instructed to take medication after eating and with a full glass of water.

Drug Interactions

Varenicline is not known to interact with any medications and has no contraindications aside from previous allergic reactions to varenicline.

Other smoking cessation therapies: Safety and efficacy in combination with other smoking cessation therapies has not been established. Coadministration of varenicline and transdermal nicotine resulted in a high rate of discontinuation due to adverse events.

Effect of smoking cessation: Pharmacokinetics or pharmacodynamics of certain drugs may be altered due to smoking cessation with CHANTIX, necessitating dose adjustment.

Pharmacokinetics

- a) Absorption: Varenicline is rapidly absorbed across the gastric mucosa, reaching a peak plasma concentration (C_{max}) in about 4 hours. After multiple oral doses, steady state is reached within 4 days. Bioavailability is unaffected by food or time-of-day dosing (food reduces the incidence and severity of nausea, a common side effect).
- b) Distribution: Varenicline exhibits linear pharmacokinetics after single or repeated doses. Plasma protein binding is low ($\leq 20\%$).
- c) Metabolism: Varenicline undergoes minimal metabolism.
- d) Excretion: Elimination half-life of varenicline is approximately 24 hours. Ninety-two percent of varenicline is excreted unchanged in the urine. Renal elimination of varenicline is primarily through glomerular filtration along with active tubular secretion possibly via the organic cation transporter, OCT2.

Adverse Events

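### The Grade 3 dose rule (8.2.3) recommends restarting study drug after full resolution, with no discretion clause and no exception for allergic reaction, the only contraindication named in 10.1

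*Combined protocol and SAP*

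**What the plan says.** Section 8.2 opens by setting its scope: "The following general guidelines apply to all adverse events except suicidal ideation or personality change". Within that scope, 8.2.3 has drug held for Grade 3 events possibly related to varenicline, with weekly assessment that may be done by telephone. Two rechallenge bullets follow.

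- Full resolution: "If the adverse event has resolved to grade 0, the patient should restart varenicline/placebo at Dose Level -1".
- Partial resolution: "If the adverse event has improved to grade 1 or 2, patients may be re-challenged", and this bullet adds that the decision is at the physician's discretion.

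The other stops in 8.2 are:

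- any Grade 4 event (8.2.4);
- a recurrence after dose reduction and rechallenge;
- a long interruption: "If treatment is skipped for more than four weeks due to toxicity, permanently discontinue varenicline/placebo";
- suicidal ideation and personality change at stated grades (8.2.7, 8.2.8);
- sleepwalking (8.2.9): "Any patient experiencing sleep walking will discontinue treatment with varenicline";
- pregnancy (8.2.10).

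For Grade 1 or 2 events, 8.2.2 leaves the choice to the physician: "varenicline/placebo dose may be continued, reduced to Dose Level -1, or be temporarily discontinued".

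Allergy appears elsewhere. The drug section, 10.1, states that varenicline "has no contraindications aside from previous allergic reactions to varenicline". Eligibility criterion 3.2.6 reads: "No allergies to and not currently using varenicline".

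**The concern.** A patient with a known varenicline allergy cannot enter the trial. A patient who develops a Grade 3 allergic reaction on study, judged possibly related and then fully resolved, meets the description of the contraindication in 10.1. The dose rule nevertheless recommends restarting. The order of the two bullets is also odd: judgement is written in for incomplete recovery and left out for complete recovery. For an allergic reaction, complete recovery says nothing about the risk of the next exposure.

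The limit of one rechallenge for Grade 3 events does not help, because it acts only after a second reaction, and that second exposure is the harm to be avoided. The lower dose does not help either, since 10.1 attaches no dose threshold to the contraindication. Patients receive the whole 12-week supply after baseline (7.3) and follow-up of the event may be by telephone, so a restart could happen without an examination or fresh dispensing.

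What is at stake is harm to an individual patient, not the validity of the comparison.

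**Working it through.** The plan gives no figure on this point, so the main check is to follow one case through the text: a Grade 3 allergic reaction, judged possibly related, resolved to grade 0 within four weeks.

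1. *Does 8.2 apply?* Yes. Its opening sentence excepts suicidal ideation and personality change only.
2. *Does another stop catch it first?* No. It is not Grade 4, sleepwalking or pregnancy, it is not a recurrence, and the interruption is not longer than four weeks.
3. *What does 8.2.3 then say?* The grade 0 bullet applies, and it says should, with no discretion clause.
4. *What does 10.1 say of the same patient?* Previous allergic reaction is the one contraindication named.
5. *What else bears on it?* Section 12.3 requires protocol therapy to end if the protocol's constraints are detrimental to the patient's health. It mentions neither allergy nor rechallenge.

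Steps 3 and 4 conflict, and nothing in section 8 resolves the conflict.

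**Size.** The enrolment target of 783 and the 1:1 allocation come from the protocol (13.6, 4.6). Every percentage below is an assumption.

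- Varenicline arm: 783 / 2 = 391.5. This is an upper bound, as it includes anyone who never takes drug.
- Patients reaching the rule, if 0.05% to 0.5% have such a reaction and it resolves in time: 391.5 × 0.0005 = 0.20; 391.5 × 0.005 = 1.96.
- Patients actually rechallenged despite 10.1 and 12.3, if 10% to 50% of those: 0.196 × 0.10 = 0.02; 1.96 × 0.50 = 0.98.
- Chance of no such patient in the whole trial, treating these as Poisson means: exp(−0.02) ≈ 98%; exp(−0.98) ≈ 38%.

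**The case against.** The best reply is that the protocol already points the other way. Naming a contraindication is in substance an instruction not to give the drug. Section 12.3 is mandatory, whereas the bullet is a recommendation inside what 8.2 calls general guidelines. The general rechallenge bullet in 8.2 is itself permissive, and any Grade 4 reaction already means a permanent stop. All of this stands, and it is why the practical effect is small. It does not make the bullet right: a site that looks up the dose rule finds a recommendation to restart and no pointer to 10.1 or 12.3.

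Three stronger readings are tempting, and the documents do not support them.

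- *The protocol orders a contraindicated rechallenge.* It does not. The word is should, and 12.3 overrides it where the patient would be harmed.
- *Blinding disables the safeguard, because 10.1 speaks of varenicline while the site holds varenicline or placebo.* Sections 8.2.3 and 8.2.9 also say varenicline and plainly mean the blinded drug, so 10.1 can be read the same way. Stopping drug needs no unblinding, so the limits in 8.3 are no obstacle.
- *Every possibly related allergic reaction, of any grade, should end treatment.* This goes beyond the defect and removes the discretion in 8.2.2. If 0.5% to 2% of all 783 patients had such a reaction (assumed), 783 × 0.005 = 3.9 to 783 × 0.02 = 15.7 would stop drug. Pairing low with low and high with high, that is about 200 (3.9 / 0.0196) down to 16 (15.7 / 0.98) stopped per rechallenge avoided, some of them on placebo. That trade-off is debatable, and the inconsistency in 8.2.3 does not require it.

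The patient information sheets, the wallet card and the package insert (cited in 9.3 for expected events) were not available, so no claim is made about what they say on allergy.

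**Conclusion.** The inconsistency is real and minor. Section 8.2.3 recommends resuming study drug after any possibly related Grade 3 event that resolves to grade 0, unless another rule in 8.2 applies. It gives no discretion in that bullet and no exception for the one contraindication the protocol names. The expected count is none or one patient rechallenged (0.02 to 1.0), which rests entirely on assumed reaction and rechallenge rates.

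A reader might infer a threat to the trial's results. There is none: sample size, power, type I error and the primary comparison are untouched. The reason to act is the possible harm to a single patient and the very low cost of removing it.

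**What to change.** 1. In the grade 0 bullet of 8.2.3, change should to may and add the physician-discretion clause that the grade 1-2 bullet already carries, keeping Dose Level -1.
2. Beside 8.2.9 and 8.2.10, add that a Grade 3 allergic or hypersensitivity reaction judged at least possibly related to study drug leads to permanent discontinuation of varenicline/placebo without rechallenge. List it among the exceptions in the opening sentence of 8.2. Grade 4 is already covered by 8.2.4.
3. Leave Grade 1-2 reactions to the physician under 8.2.2, read with the contraindication in 10.1.

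Change 1 alone would remove the recommendation but still permit rechallenge after a Grade 3 allergic reaction; change 2 closes that.

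The cost is one reworded bullet, one added sentence and one added exception, with no extra patients, visits or tests. The downside is that a few patients in either arm with resolved Grade 3 events may not restart drug. For allergic reactions, applying the assumed 0.05% to 0.5% to both arms gives 783 × 0.0005 = 0.4 to 783 × 0.005 = 3.9 patients; for other Grade 3 events the documents give no basis for a number. All remain in follow-up (12.1), and those who have surgery stay in the analysis by assigned arm (13.1.1).
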